6.6.2 Laboratory Data

Safety laboratory data at each study visit and changes from baseline will be summarized by treatment group. Laboratory parameters will be reported in original units without conversion, see Table 9-2.

In addition, clinical laboratory summaries will be presented by treatment group including: (i) incidence of significant abnormalities by visit; (ii) tables summarizing the frequencies of subjects below, within, and above the normal reference ranges at baseline and end of study; and (iii) tables displaying baseline to end of study shifts in each laboratory value (shifts between below, within or above normal range).

All laboratory data will be provided in data listings.

A subset listing will be presented for all abnormal laboratory values.

6.6.3 Vital Signs and Physical Examinations

The actual value and change from baseline to each on study evaluation will be summarized for vital signs.

By-subject listings of vital sign measurements will be presented in data listings.

6.6.4 Electrocardiogram

Not applicable.

7 CHANGES TO PLANNED ANALYSES

The following are changes between the protocol-defined statistical analyses and those presented in this statistical analysis plan:

The FAS will be the primary analysis set for the analysis of the primary and secondary efficacy endpoints rather than ITT. FAS includes all randomized subjects who received at least 1 dose of study medication. Subjects will be analyzed according to their randomized treatment.

Safety analysis set will be the primary set for the analysis of the safety parameters and it includes all randomized subjects who received at least 1 dose of study medication. Subjects will be analyzed according to their actual treatment. Actual treatment is defined as the treatment received for most of the days during the treatment phase of the study.

The data of NYHA functional class will be considered to be ordinal categorical values in the analysis. Change from baseline in NYHA functional class will be evaluated between the treatment groups using logistic regression adjusted for the baseline NYHA functional class (stratification variable). Missing data will be imputed in an analogous fashion to the primary outcome including sensitivity analyses to define the range of uncertainty imposed by missing data (worst case scenario and complete case analysis) but for categorical variables.

The data of escalation of routine clinical treatments for PAH will be analyzed as a binary categorical variable (yes / no escalation). A Cochran-Mantel-Haenszel (CMH) test with adjustment for the stratification factor baseline NYHA functional class will be used to test the null hypothesis of no treatment effect during the trial for famotidine vs. placebo with regards to the proportion of subjects with an escalation of routine clinical treatments for PAH. Missing data will be imputed in an analogous fashion to the primary outcome including sensitivity analyses to define the range of uncertainty imposed by missing data (worst case scenario and complete case analysis) but for categorical variables.

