2.2 Randomization Methodology

A total of 80 subjects are to be randomly assigned in a 1:1 ratio to one of two arms using permuted block randomization: (1) placebo or (2) famotidine. Subject randomization will be stratified by NYHA/WHO Functional Class (NYHA/WHO Functional Class II versus Class III/IV) to ensure balanced representation of this important marker of severity. A randomization code will be computer-generated by contract research organization (CRO) Axio Research, LLC. Subjects meeting study entry criteria will be randomized via an interactive web response system (IWRS). The randomization schedule will be generated by the randomization statistician at Axio Research (who is not on the project team) or designee and maintained in a secure and limited-access location separate from the study investigator and members of the project team. The study subject, investigative staff, the Sponsor, the Sponsor study team (includes contractors and vendors), excluding the unblinded study site pharmacist will be blinded to treatment assignments during the study.

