6.2.3 Adjustments for Covariates

Subject randomization will be stratified by NYHA/WHO Functional Class (NYHA/WHO Functional Class II versus Class III/IV) to ensure balanced representation of this important marker of severity.

For continuous outcome variables, baseline values of the dependent variable and NYHA functional class (as a binary stratification variable) will be included in the statistical model .

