6.4.2.2 NYHA functional class

Summary tabulations of the number and percentage of participants within each NYHA functional class for each visit will be presented by treatment group. NYHA functional class will be evaluated between the treatment groups using ordinal logistic regression adjusted for the baseline NYHA functional class (stratification variable). The odds ratio with 95% CIs will be reported.

Missing data will be imputed in an analogous fashion to the primary outcome including sensitivity analyses to define the range of uncertainty imposed by missing data (worst case scenario and complete case analysis) but for categorical variables [3]. The worst case scenario for NYHA functional class will be assumed to be IV.

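### The SAP names two outcomes for the NYHA analysis, class and change in class, and adjusts both only for the II versus III/IV stratum

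*SAP*

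**What the plan says.** **Outcome and model.** SAP 6.4.2.2, the methods section for this endpoint, says: "NYHA functional class will be evaluated between the treatment groups using ordinal logistic regression adjusted for the baseline NYHA functional class (stratification variable". SAP 7 first states "The data of NYHA functional class will be considered to be ordinal categorical values in the analysis" and then: "Change from baseline in NYHA functional class will be evaluated between the treatment groups using logistic regression". Section 7 is current text, since it introduces itself as listing "changes between the protocol-defined statistical analyses and those presented in this statistical analysis plan". The endpoint lists in SAP 3.1 and 6.4.2 (and in Protocol 3) are introduced by the word change. The opening of SAP 6.4 is not. Neither 6.4.2.2 nor 7 names the visit for the regression. The objective in SAP 1.2 is at 24 weeks, and the class is recorded at baseline, Week 12 and Week 24.

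**Covariate.** Section 7 uses "logistic regression adjusted for the baseline NYHA functional class (stratification variable", the same covariate as 6.4.2.2. SAP 2.2 defines that variable: randomisation is "stratified by NYHA/WHO Functional Class (NYHA/WHO Functional Class II versus Class III/IV". Protocol 9.4.3 adjusted every secondary endpoint for two things, its baseline value and the stratum. The SAP keeps both for BNP, right ventricular diameter, TAPSE and emPHasis-10 (6.4.2.1 and 6.4.2.3 to 6.4.2.5). For NYHA class only the stratum is left. Class IV patients are eligible (Protocol 5.1).

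**The concern.** Week 24 class and change in class are different outcomes with different odds ratios. With both in the SAP and no order of precedence, whoever programs the table has to choose, and the choice could be made after unblinding.

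The covariate makes the difference matter. If exact baseline class were in the model, the class and change versions would be close. With III and IV merged, they rank the same participants differently. The merged term also leaves the III versus IV difference, which predicts the outcome and is already recorded, in the unexplained variation.

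**Working it through.** The documents give no power or effect size for NYHA class, so there is no figure of the plan's to reproduce first.

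**1. Where the two outcomes part.** SAP 5.2 defines change as the value at the time point minus the baseline value. Take four participants who all fall in the III/IV stratum:

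| Baseline | Week 24 | Outcome under 6.4.2.2 | Outcome under 7 |
|---|---|---|---|
| III | II | II | 2 − 3 = −1 |
| IV | III | III | 3 − 4 = −1 |
| III | IV | IV | 4 − 3 = +1 |
| IV | IV | IV | 4 − 4 = 0 |

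Rows 1 and 2 differ under the class model and tie under the change model. Rows 3 and 4 do the reverse. The covariate has the same value in all four rows, so it cannot repair this.

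The worst-case analysis is affected too. It sets a missing class to IV. Under the class model every such participant has the same outcome. Under the change model the value is 4 − 2 = +2, 4 − 3 = +1 or 4 − 4 = 0, for baseline II, III or IV.

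**2. How much it can matter.**

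- From the documents: 80 participants, 1:1 within strata, two-sided 0.05.
- Assumed: class IV share of 0%, 5% or 15% (II/III/IV mixes 50/50/0, 50/45/5, 45/40/15%); a latent logistic model for Week 24 class with baseline shifts 0, 2.5 and 5 for II, III and IV and cut-points −1.7, 1.2 and 4.0; true odds ratio for a worse class 1.0 or 0.4.
- Method: 400 trials per scenario, maximum likelihood, likelihood-ratio test. Class and change are both fitted as ordinal models with treatment and the two-level stratum.

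| Class IV share | True OR | Median OR, class / change | Median ratio of the two ORs (90th percentile) | Significance disagrees |
|---|---|---|---|---|
| 0% | 1.0 | 1.002 / 1.002 | 1.013 (1.043) | 1.0% |
| 0% | 0.4 | 0.385 / 0.382 | 1.024 (1.081) | 1.5% |
| 5% | 1.0 | 1.007 / 0.992 | 1.111 (1.300) | 4.3% |
| 5% | 0.4 | 0.393 / 0.378 | 1.101 (1.310) | 10.7% |
| 15% | 1.0 | 1.028 / 1.021 | 1.166 (1.496) | 6.0% |
| 15% | 0.4 | 0.434 / 0.404 | 1.180 (1.548) | 16.5% |

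A second simulation, with true OR 0.35 and the same three shares, gave disagreement of 2.5%, 11% and 17.5%.

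**3. Cost of an open choice when there is no effect.** The chance that at least one model is significant is (p_class + p_change + disagreement)/2. At 15% class IV this is (0.045 + 0.055 + 0.060)/2 = 0.08, against 0.045 and 0.055 for the single models.

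**4. Merged versus full baseline class.** Power for Week 24 class at true OR 0.4:

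| Class IV share | Stratum only | Full class (II, III, IV) | Gain |
|---|---|---|---|
| 0% | 0.552 | 0.552 | 0 |
| 5% | 0.562 | 0.583 | 0.021 |
| 15% | 0.460 | 0.530 | 0.070 |

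Both models were fitted to the same trials, so the Monte Carlo standard error of the gain is √[(d − gain²)/400], where d is the share of trials in which they disagree. At 5%: √[(0.090 − 0.021²)/400] = 0.015. At 15%: √[(0.145 − 0.070²)/400] = 0.019. The gain is clear at 15% and within simulation error at 5%. The simulation with true OR 0.35 gave gains of 0, about 0.035 and about 0.065. Full class did not lower power in any of these runs.

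**The case against.** **The conflict may be loose wording.** Section 7 says it reports what the SAP contains, so 6.4.2.2, as the detailed methods section, is the natural text to follow. That is reasonable, but it is not written down, and 3.1 and 6.4.2 lean towards change.

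**A reader might infer that section 7 prescribes a binary improved/not improved model, which would discard information.** The documents do not support this. Section 7 calls the NYHA data ordinal, and it uses the word binary for escalation of treatment but not for NYHA. Ordinal versus binary is only an ambiguity, left by omitting one word and the categories of change. Were it read as binary, it would disagree with the class model on significance in about 18 to 23% of the simulated trials at OR 0.4. That is not the size of the conflict actually in the text.

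**Adjusting for the randomisation stratum is standard.** This stands: the stratum alone is a valid covariate, and for this endpoint the authors may have seen the baseline value and the stratum as one variable. They are not, because the stratum has two levels and the class has three. The rule "NYHA functional class (as a binary stratification variable) will be included in the statistical model" in SAP 6.2.3 is worded for continuous outcomes. The merging for NYHA therefore follows from the label in 6.4.2.2 and the definition in 2.2.

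**Class IV may be rare.** This also stands. Of 80 participants, 5% is 4 and 15% is 12. With none, full class and stratum are the same covariate.

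**Conclusion.** The SAP is wrong as written on one matter: it gives class in one place and change in another as the outcome of the same analysis, with no precedence. The baseline covariate is a separate and lesser matter. It drops a term that the protocol specified, and restoring it is a free improvement, not the correction of an invalid analysis.

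It would go too far to say that the NYHA result will depend on the section followed. It can. With no class IV at baseline the two ordinal odds ratios differ by a median of 1 to 2%, and significance disagrees in 1.0 to 2.5% of trials. With 5 to 15% class IV and a true OR of 0.35 to 0.4, disagreement is about 11 to 17% and the power gain from full class is about 0.02 to 0.07. These figures rest on the assumed class mix, transition model and effect, none of which the documents give.

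NYHA class is one of six secondary endpoints, with no multiplicity adjustment (SAP 6.2.4). The primary 6MWD analysis is not touched.

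**What to change.** State one analysis in SAP 3.1, 6.4.2, 6.4.2.2 and 7: proportional-odds regression of Week 24 NYHA class on treatment, adjusted for actual baseline class (II, III, IV), reporting the common odds ratio with its 95% CI. Actual class determines the stratum, so no separate stratum term is needed. Week 24 class fits the objective in SAP 1.2. Remove the change wording for NYHA from 3.1 and 6.4.2, and record in 7 that this departs from the change endpoint in Protocol 3 and the linear regression in Protocol 9.4.3. Apply the same outcome in the imputed, worst-case and complete-case analyses.

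Fix in advance what happens if class IV is too sparse for its own coefficient, for example by entering baseline class as a single linear score (2, 3, 4). A score plus the stratum would not help. With the stratum coded 0 for II and 1 for III/IV, score − 2 − stratum equals 0, 0 and 1 for II, III and IV, so that pair is the three-level factor again.

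The cost is SAP wording before unblinding. No new data are needed, because full class is already collected at baseline and Week 24.

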9 APPENDICES

9.1 Schedule of Assessments

Table 9-1: Schedule of assessments

	Baseline	Randomization	Phone Visit Week 4	Week 12	Week 24	
Visit #	1	Non-visit	PH	2	3	
Day #	-14 to -1	-1	0	28 ± 7	84 ± 7	168 ± 7
Inclusion/Exclusion Criteria	X					
Informed Consent	X					
History and physical exam						
Demographics	X					
Medical history	X					
Symptom assessment	X			X	X	
Concomitant medications	X			X	X	
Vital Signs & Weight	X			X	X	
Physical Examination	X			X	X	
Safety laboratories						
Laboratory Draw	X				X	
Comprehensive metabolic panel	X				X	
Complete blood count	X				X	
Mass-Spectrometry for H ₂ antagonists	X				X	

Pregnancy test if premenopausal	X				X
Endpoint assessment					
6 minute-walk distance (primary)	X			X	X
echocardiogram	X				X
emPHasis-10 score	X			X	X
BNP	X				X
NYHA functional class	X			X	X
Study Procedures					
Dispense study drug		X		X	
Start study drug			X		
Study drug adherence				X	X
Study drug compliance				X	X
Adverse events	X			X	X
Study Termination					X
Sub-study components					
Right heart catheterization (n=20)	X				X
Cardiopulmonary Exercise Test (n=10)	X				X
Miscellaneous					
Data Safety Monitoring Board			Semi-annually		

As per clinical practice guidelines, patients will be seen every three months with blood work and six-minute walk testing. These elements (visit, laboratory draw, comprehensive metabolic panel, complete blood count, BNP, pregnancy test, 6 minute-walk distance, and NYHA functional class) will be collected as part of routine medical care and abstracted from the medical record as research endpoints. Echocardiograms are often part of routine medical care and will be abstracted from the medical record as research endpoints; however, the frequency may be influenced by the study. To avoid any concern about overlap, any

echocardiogram occurring more frequently than annually will be considered research. It is anticipated that 1 of the 2 echocardiograms will fit this research definition. Other research elements include mass spectrometry for H2 antagonists, the emPHasis-10 score, study procedures, and sub-study components.

9.2 Estimands

Not applicable.

9.3 Laboratory Conversion Factors

Laboratory parameters will be reported in original units without conversion, see Table 9-2.

Table 9-2: Laboratory parameters

Parameter (unit)
Sodium (mEq/L)
Potassium (mEq/L)
BUN (mEq/L)
Creatinine (mEq/L)
WBC (thou/uL)
Hemoglobin (g/dL)
Platelets (thou/uL)
BNP (pg/mL)
Calcium (mg/dL)

